Endpoints:	
Primary
 

Frequency and severity of ocular AEs in the treatment and contralateral eyes

 
Secondary
 

Frequency and severity of non-ocular AEs

Changes in ophthalmic examination findings

Change in BCVA

Changes in infrared imaging

Changes in OCT findings

Changes in safety parameters, including vital sign measurements, physical examination findings, ECG and laboratory parameters

Characterize the PK profile of QR-110 in serum

Change in light sensitivity to red FST

Change in light sensitivity to blue FST

Change in amplitude to white PLR

Change in latency to white PLR

 
Exploratory

Study Drug, Dosage and Mode of Administration:	QR-110 Solution for IVT Injection, Up to 3 dose levels will be tested (loading dose/maintenance dose): 160 µg/80 µg, 320 µg/160 µg, and 500 µg/270 µg. QR-110 will be administered every 3 months for a total of 4 doses per subject.
Duration of Treatment:	12 months
Reference Therapy, Dosage and Mode of Administration:	Not applicable

Criteria for Evaluation:	
Safety and Tolerability:	

• Frequency and severity of ocular and non-ocular AEs

• Ophthalmic examination findings

• BCVA

• Infrared imaging

• OCT

• Vital sign measurements

• Physical examination findings

• ECG

• Laboratory parameters

PK:	

• Subjects will provide blood samples for presence of QR-110 at multiple time points

Efficacy:	

• BCVA

• White PLR

• Red FST

• Blue FST

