Statistical Methods:	
Baseline demographics and disease characteristics, safety and efficacy endpoints will be summarized descriptively by dose group and for all subjects combined. Continuous efficacy endpoints will be summarized and may be analyzed using appropriate parametric or nonparametric inference tests. Serum concentrations of QR-110 will be summarized by dose level and time point. To determine the PK profile of IVT injections at the different dose levels of QR-110, the following PK parameters will be calculated if sufficient data are available for each dose:
 

• <math>AUC_{0-\infty}</math>: Area under the curve to infinity will be calculated based on the last observed concentration <math>C_{last}</math> (obs) using formula: <math display="block">AUC_{0-\infty} = AUC_{last} + C_{last}(\text{obs})/\lambda_z, \text{ if feasible.}</math>

• <math>AUC_{0-t_{last}}</math>: Area under the curve to the final sample with a concentration greater than lower limit of quantification (LLOQ) will be calculated based on the last observed concentration using the linear trapezoidal method.

• <math>C_{max}, C_0</math>: The maximum and minimum serum concentrations will be taken directly from the data.

• <math>T_{max}</math>: Time to <math>C_{max}</math> will be taken directly from the data.

• <math>T_{1/2}</math> (if measurable serum levels are obtained): The terminal elimination half-life will be estimated by non-linear regression analysis of the terminal elimination slope, if feasible.

• <math>CL</math>: Serum clearance will be estimated using the formula: <math>CL = \text{Dose}/AUC_{0-\infty}</math>.

• <math>V_d</math> (if measurable serum levels are obtained and an elimination rate constant (<math>\lambda_z</math>) is estimable): Apparent volume of distribution at steady state of the drug will be determined from trough levels.

 
Any p values that will be calculated according to the analysis plan will be interpreted in view of the exploratory nature of the study. Details on statistical analyses will be included in the Statistical Analysis Plan.

-----------------------------	---

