### 7.1 Visit and Assessment Windows

The timing of assessments, procedures and sample collections are outlined in the protocol. For those procedures for which a specific time point post dose is required (eg, PK blood draws), the protocol refers to nominal times. Actual times for such assessments are to be recorded in the source documentation and in the electronic Case Report Forms (eCRFs), and if any time points are missed, the reasons are also to be recorded. Recording of actual times is not required for assessments for which only a study visit and not a specific time is stated in the protocol.

Each study visit may take up to 1 day, or may be conducted in multiple consecutive days instead of 1 full day, at the discretion of the Investigator.

Visits 7 days post injections have a visit window of +/- 3 days. Visits 1 month and 2 months post injections have a visit window of +/- 7 days, and dosing visits have a visit window of +/- 10 days. The visit 14 days post-dose 1 is conducted by telephone and has a visit window of +/- 3 days.

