### **8.4      Pharmacokinetic Evaluations**

Samples for PK analysis will be collected as indicated per the SOE.

Blood samples will be obtained from all subjects to assess PK parameters of QR-110 ( $AUC_{0-\infty}$ ,  $AUC_{0-t_{last}}$ ,  $C_{max}$ ,  $C_0$ ,  $T_{max}$ ,  $T_{1/2}$ ,  $CL$ ,  $V_d$ ) pre- and post-dosing as indicated per the SOE (Appendix 1).  $T_{1/2}$  and  $V_d$  will only be evaluated if measurable serum levels are obtained.

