## **10.7 Pharmacokinetics Analyses**

To determine the PK profile of IVT injections at the different dose levels of QR-110, the following PK parameters will be calculated if sufficient data are available for each dose:

- $AUC_{0-\infty}$ : Area under the curve to infinity will be calculated based on the last observed concentration ( $C_{last}(obs)$ ) using formula:  $AUC_{0-\infty}=AUC_{last}+C_{last}(obs)/\lambda z$ , if feasible.
- $AUC_{0-t_{last}}$ : Area under the curve to the final sample with a concentration greater than lower limit of quantification (LLOQ) will be calculated based on the last observed concentration using the linear trapezoidal method.
- $C_{max}$ ,  $C_0$ : The maximum and minimum serum concentrations will be taken directly from the data.
- $T_{max}$ : Time to  $C_{max}$  will be taken directly from the data.

- $T_{1/2}$  (if measurable serum levels are obtained): The terminal elimination half-life will be estimated by non-linear regression analysis of the terminal elimination slope, if feasible.
- CL: Serum clearance will be estimated using the formula:  $CL = \text{Dose}/AUC_{0-\infty}$ .
- $V_d$  (if measurable serum levels are obtained and an elimination rate constant ( $\lambda_z$ ) is estimable): Apparent volume of distribution at steady state of the drug will be determined from trough levels.

Serum concentration below LLOQ prior to dose for the assay will be set to zero for the PK analysis. For other cases concentrations below LLOQ will be set for non-informative missing. Exact procedure for imputation of data will be described in the SAP.

All samples obtained from all cohorts will be analyzed to avoid bias in data presentation.

Sparse sampling analysis may be used to mitigate the risk of insufficient data to create individual profiles.

Drug concentrations will be summarized by nominal time point if 3 or more values are available. Descriptive statistics for PK parameters will be performed if  $\geq 50\%$  of subjects have evaluable data and number of values to summarize is  $\geq 3$ .

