12.8 Clinical Laboratory Data

Clinical laboratory data including hematology, coagulation, serum chemistry and urinalysis are collected at specified visits. Other lab tests which are collected and will be summarized include Complement C4 NEPH, C-reactive protein (CRP), complement total, and erythrocyte sedimentation rate. The quantitative variables will be summarized by dose group and for all subjects with continuous descriptive statistics at each visit and time point where appropriate. The qualitative variables (counts and percentages) will be summarized by dose group and for all subjects at each visit and time point where appropriate. Change from baseline will also be summarized by dose group and for all subjects.

13. Pharmacokinetic Analyses

Pharmacokinetic (PK) analyses will be primarily performed on the PK population with observed data only. To determine the PK profile of IVT injections at the different dose levels of QR-110, the following PK parameters will be calculated if sufficient data are available for each dose:

- $AUC_{0-\infty}$: Area under the curve to infinity will be calculated based on the last observed concentration ($C_{last(obs)}$) using formula: $AUC_{0-\infty} = AUC_{last} + C_{last(obs)} / \lambda z$, if feasible.
- $AUC_{0-t_{last}}$: Area under the curve to the final sample with a concentration greater than lower limit of quantification (LLOQ) will be calculated based on the last observed concentration using the linear trapezoidal method.
- C_{max} , C_0 : The maximum and minimum serum concentrations will be taken directly from the data.
- T_{max} : Time to C_{max} will be taken directly from the data.
- $T_{1/2}$ (if measurable serum levels are obtained): The terminal elimination half-life will be estimated by non-linear regression analysis of the terminal elimination slope, if feasible.
- CL : Serum clearance level will be estimated using the formula: $CL = Dose / AUC_{0-\infty}$.
- V_d (if measurable serum levels are obtained and an elimination rate constant (λz) is estimable): Apparent volume of distribution at steady state of the drug will be determined from trough levels.

Serum concentration below LLOQ prior to dose for the assay will be set to zero for the PK analysis. For other cases concentrations below LLOQ will be set to one half of LLOQ.

All samples obtained from all cohorts will be analyzed to avoid bias in data presentation.

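### C0 is defined as the minimum concentration with no interval, which can make it zero in every subject, and AUC0-inf and CL are not tied to the first injection

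*Protocol*

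**What the plan says.** Cmax and C0 share one definition in the protocol synopsis, protocol 10.7 and SAP 13: "The maximum and minimum serum concentrations will be taken directly from the data". None of the three states the interval over which the minimum is taken. The protocol's List of Abbreviations gives C0 as the trough value, and the same PK sections say that Vd will be determined from trough levels. Protocol 10.7 and SAP 13 both plan geometric means and coefficients of variation for C0, the two areas, CL and Vd.

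The SAP's rules for values below LLOQ are: "Serum concentration below LLOQ prior to dose for the assay will be set to zero for the PK analysis" and "For other cases concentrations below LLOQ will be set to one half of LLOQ". Protocol 8.4 calls for blood samples before and after dosing.

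The planned areas are AUC0-inf and AUC0-tlast, with CL = Dose/AUC0-inf. No area over the dosing interval is listed. The scope sentence opens with "To determine the PK profile of IVT injections at the different dose levels of QR-110" and continues: "the following PK parameters will be calculated if sufficient data are available for each dose". The regimen is repeated: "QR-110 will be administered every 3 months for a total of 4 doses per subject". Each dose level combines a loading dose with smaller maintenance doses (160/80 µg low, 320/160 µg mid). SAP 3 states that no subject was treated at the high level.

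**The concern.** These definitions suit a single dose, and the trial gives up to four.

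A trough has to be tied to the end of a dosing interval. A minimum with no interval can instead pick up the drug-free sample taken before the first injection, which carries no information about QR-110.

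AUC0-inf divided into the dose estimates clearance only when the area comes from that dose alone. After a repeat injection it also holds whatever remains from earlier ones. Clearance could then appear to fall from dose 1 to dose 2 with no change in kinetics.

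At stake are the C0, AUC0-inf and CL tables, and Vd so far as it relies on troughs. Serum PK is a secondary objective, and the primary safety endpoint is not touched.

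**Working it through.** The documents state no PK result, so there is no figure to reproduce.

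**C0 under the possible readings.** Protocol 2.2.2 reports no earlier clinical study of QR-110 IVT solution, so subjects are taken as drug-naive on Day 1. A Day 1 pre-dose sample should then be below LLOQ and is set to 0. Any other value below LLOQ becomes LLOQ/2, which is above 0, and any measurable value is higher still.

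- Minimum over the whole study: 0 in every subject, whatever the kinetics.
- Minimum over a dose 1 profile that includes its pre-dose sample: also 0 in every subject.
- Minimum within the interval for doses 2, 3 or 4: a real trough if the pre-dose sample is measurable, and 0 only if that sample is below LLOQ and counts as pre-dose under the zero rule.

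A geometric mean is the exponential of the mean log. One zero makes it 0 as a product, or undefined on the log scale. Under the first two readings this happens with certainty and needs no assumption about half-life.

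**AUC0-inf and CL after a repeat dose.** Inputs:

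- Loading:maintenance ratio = 160/80 = 320/160 = 2 (SAP 3).
- Dosing interval of 3 months, taken as 91 days.
- Serum half-life t: not in the documents, so an assumed range is used.
- Mono-exponential decline and linear superposition: assumed.

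The fraction left after one interval is f = 2^(-91/t). The area from dose k to infinity is (dose k + residual)/CL, so its ratio to that dose's own Dose/CL is:

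- dose 2: 1 + 2f
- dose 3: 1 + f + 2f²
- dose 4: 1 + f + f² + 2f³

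Estimated CL over true CL is the inverse of the ratio.

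| Assumed half-life | f | Dose 2 | Dose 3 | Dose 4 | CL ratio, dose 2 |
|---|---|---|---|---|---|
| 7 days | 0.0001 | 1.000 | 1.000 | 1.000 | 1.000 |
| 14 days | 0.011 | 1.022 | 1.011 | 1.011 | 0.978 |
| 30 days | 0.122 | 1.244 | 1.152 | 1.141 | 0.804 |
| 60 days | 0.350 | 1.699 | 1.594 | 1.557 | 0.589 |

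Solving 2f = excess for t, the dose 2 overstatement reaches 1% at a half-life of about 12 days, 5% at about 17, 20% at about 27 and 50% at about 46.

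Protocol 7.1 says "dosing visits have a visit window of +/- 10 days". Shifting the interval to 81 or 101 days moves the 30-day dose 2 figure to 1.31 or 1.19.

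**Check on the alternative area.** Area over the dosing interval after dose 2, relative to Dose/CL, is (1 + 2f)(1 - f). At 30 days that is 1.244 × 0.878 = 1.09. It contains less carry-over than AUC0-inf, but not none.

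**The case against.** The strongest counter-argument is that the text can be read sensibly. The abbreviation list and the Vd wording point to a trough. On a per-interval reading, the minimum at doses 2 to 4 can be that trough, and a zero at dose 1 is simply correct. This is a fair account of what was probably meant. It does not remove the problem, because the operational definition, stated three times, says minimum and names no interval.

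A reader might infer that AUC0-inf is planned after every injection. The documents do not say so. The scope sentence opens with dose levels, results are tabulated by dose group, and AUC0-inf is computed only if feasible. Reading it by dose level still leaves a gap: each level contains two different doses, so the dose in CL = Dose/AUC0-inf is not identified.

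A reader might also infer that C0 must be the pre-study zero and that exposure after doses 2 to 4 will be overstated. These two consequences pull apart. A pre-dose sample below LLOQ leaves no observed carry-over. Measurable carry-over makes a per-interval minimum a true trough. They occur together only under a whole-study minimum, which no sentence specifies. No half-life is given, and protocol 2.4 expects low systemic absorption. Nor can f be deduced from the 2:1 loading ratio, since protocol 2.4.1 refers the dose selection to the Investigator's Brochure.

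Nor is accumulation hidden. Concentrations are summarised by nominal time point when at least 3 values exist, so any later pre-dose samples would be shown there.

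Finally, protocol 10.7 defers exact detail to a Pharmacokinetic Analysis Plan, which was not available here and may settle some of this. SAP 13 does not repeat that pointer, and SAP 1 says its methods supersede the protocol's.

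**Conclusion.** The C0 part holds as a conflict of definitions. Under two literal readings, C0 is 0 in every drug-naive subject and its planned geometric mean is zero or undefined. This rests only on the stated rules and on a Day 1 pre-dose sample being taken. The sampling schedule is not in the supplied text.

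The AUC0-inf and CL part holds conditionally. It needs these parameters to be computed after doses 2 to 4 and serum drug to be measurable at 3 months. Under the mono-exponential assumption, the dose 2 excess is nil to about 2% for half-lives up to 14 days and about 24% at 30 days, where CL reads about 20% low. Which of these applies cannot be told from the documents.

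The documents do not support saying that exposure after repeat doses will be overstated, or that the trial cannot show accumulation. The consequence is confined to the secondary C0, AUC0-inf and CL tables and whatever is derived from them. It is still worth correcting, because the change is cheap.

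**What to change.** In SAP 13, and in protocol 10.7 for consistency:

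1. Define C0 as the pre-dose concentration at doses 2, 3 and 4 (Months 3, 6 and 9) where sampled. Tabulate it by dose number and exclude the Day 1 pre-dose sample.
2. State how zeros enter the geometric mean, for example by reporting the number below LLOQ with the median and range. Say whether the pre-dose zero rule applies at later doses.
3. State whether the scope phrase means each injection or each dose level, and that AUC0-inf, CL and the parameters derived from them refer to the first injection only.
4. For later injections, report a dose-normalised AUC over a common sampled interval, with its ratio to dose 1. Note that this area may still contain some carry-over and should not be converted to CL.

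The cost is wording and programming in the SAP or PK analysis plan. No new samples are needed if pre-dose samples at Months 3, 6 and 9 are already scheduled. That should be checked against the Schedule of Events.

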## LIST OF TABLES

## LIST OF FIGURES

## LIST OF ABBREVIATIONS AND DEFINITIONS OF TERMS

Abbreviation	Definition
A	Adenine
AE	Adverse Event
ALT	Alanine Aminotransferase
AON	Antisense Oligonucleotide
AREDS	Age-Related Eye Diseases Study
ARLNS	Clinical Lens Grading System
AST	Aspartate Aminotransferase
AUC 0-∞	Area under the curve 0 hour to infinity
AUC 0-tlast	Area under the curve 0 hour to time of the last measurable concentration
BCVA	Best-corrected Visual Acuity
BUN	Blood Urea Nitrogen
C	Cytosine
CBC	Complete Blood Count
CEP290	Centrosomal Protein 290 kDa
CEP290	CEP290 gene
CF	Counting Fingers
CFR	Code of Federal Regulations
CH50	C4, Hemolytic complement 50
CKD-EPI	Chronic Kidney Disease Epidemiology Collaboration
CL	Clearance
CRP	C Reactive Protein
C max	Maximum Concentration
C 0	Trough Value
CSR	Clinical Study Report

DMC	Data Monitoring Committee
EC	Ethics Committee
ECG	Electrocardiogram
eCRF	Electronic Case Report Form
eGFR	Estimated Glomerular Filtration Rate
EOS	End of Study
ERG	Electroretinogram
ESE	Exonic Splicing Enhancer
ESR	Erythrocyte Sedimentation Rate
FDA	Food and Drug Administration
FST	Full-field Stimulus Testing (also, Full-field Stimulus Threshold Testing or Full-field Scotopic Threshold Testing)
G	Guanine
GCP	Good Clinical Practice
GGT	Gamma-Glutamyl Transferase
GLP	Good Laboratory Practice
HM	Hand Motion
IB	Investigator's Brochure
ICH	The International Council on Harmonisation
INR	International Normalized Ratio
IOP	Intraocular Pressure
iPSC	Induced Pluripotent Stem Cells
IRB	Institutional Review Board
IVT	Intravitreal
LCA	Leber's Congenital Amaurosis
LDH	Lactic Dehydrogenase

LLOQ	Lower Limit of Quantification
LogMAR	Logarithm of the Minimum Angle of Resolution
LP	Light Perception
MedDRA	Medical Dictionary for Regulatory Activities
mRNA	Messenger Ribonucleic Acid
NEHD	Normalized Equivalent Human Dose
NIH	National Institute of Health
OCI	Oculomotor Instability
OCT	Optical Coherence Tomography
ONL	Outer Nuclear Layer
PBS	Phosphate Buffered Saline
p.Cys998X	c.2991+1655A>G mutation in the CEP290 gene
PD	Pharmacodynamic
PK	Pharmacokinetic
PLR	Pupillary Light Reflex
ProQR	ProQR Therapeutics
PT	Preferred Term
RNA	Ribonucleic Acid
SAE	Serious Adverse Event
SAP	Statistical Analysis Plan
SOC	System Organ Class
SOE	Schedule of Events
SOP	Standard Operating Procedure
SUN	Standardization of Uveitis Nomenclature
SUSAR	Suspected Unexpected Serious Adverse Reaction
TEAE	Treatment Emergent Adverse Event
TLF	Table, Listing and Figure

$T_{1/2}$	Terminal half-life
$T_{max}$	Time of maximum concentration
$T_{min}$	Time of minimum concentration
ULN	Upper Limit of Normal
US	United States
$V_d$	Volume of Distribution
WOCBP	Women of Childbearing Potential

## 2.0 INTRODUCTION

ProQR Therapeutics (ProQR) is developing an antisense oligonucleotide (AON) product, QR-110, for the treatment of patients with Leber's congenital amaurosis (LCA) due to the c.2991 +1655A>G mutation (p.Cys998X or IVS26+1655A>G) in the Centrosomal Protein of 290kDa (*CEP290*) gene. Leber's congenital amaurosis is a severe inherited retinal degenerative disease resulting in blindness, often in early childhood. In patients with LCA due to the p.Cys998X mutation in the *CEP290* gene (subsequently referred to as *CEP290* p.Cys998X mutation), visual symptoms are usually detectable before 1 year of age and further deterioration over time has also been reported ([den Hollander 2008](#), [Yzer 2012](#)). Patients show severe vision disturbances from an early age and slow progressive loss of remaining vision ([Cideciyan 2007](#), [Cideciyan 2011](#), [McAnany 2013](#)). There are currently no approved therapies for the treatment of LCA due to the *CEP290* p.Cys998X mutation and a large unmet medical need exists. The primary goal of the development plan for QR-110 is to provide a treatment to overcome the genetic defect in patients with at least one *CEP290* allele containing the *CEP290* p.Cys998X mutation, resulting in functional vision restoration or preservation. The intended route of administration is intravitreal (IVT) injection.

### 2.1 Leber's Congenital Amaurosis

Leber's congenital amaurosis is a non-syndromic retinopathy that affects both cone and rod photoreceptor cells of the retina. It is a rare autosomal recessive disorder, reported to be the most severe and one of the earliest onset forms of vision loss in children, with detection of disease symptoms as early as the first year of life. The symptoms and signs include severe and early vision loss, sensory nystagmus (involuntary eye movements), abnormalities of pupil reactions, oculo-digital sign, and nondetectable photoreceptor electrical signals on electroretinogram (ERG). There are approximately 20 genes identified to date in which mutations are causative for LCA ([den Hollander 2008](#), [Estrada-Cuzcano 2011](#), [Kmoch 2015](#)), and the LCA classification is based on the disease causing gene. The most frequently mutated LCA gene is *CEP290*, with mutations accounting for about 15% to 30% of LCA cases ([Coppieters 2010](#), [den Hollander 2008](#), [den Hollander 2006](#), [Perrault 2007](#), [Stone 2007](#)).

The *CEP290* gene is located on the long (Q) arm of chromosome 12 and codes for CEP290 protein, which has an important role in centrosome and cilia development. The most frequently occurring *CEP290* mutation associated with retinal dystrophy in Caucasians, especially in European countries and the United States (US), is a change in intron 26 of the *CEP290* gene (p.Cys998X) ([Stone 2007](#), [den Hollander 2006](#), [Perrault 2007](#), [Littink 2010](#)). This mutation creates a cryptic splice donor site in intron 26 which results in the inclusion of an aberrant exon (exon-X) of 128 bases in the mutant *CEP290* messenger ribonucleic acid (mRNA). This cryptic exon introduces a premature stop codon, predicted to render CEP290 a truncated protein. The mutation has been found in homozygosity or compound heterozygosity in patients with *CEP290* LCA ([Cideciyan 2007](#), [den Hollander 2006](#), [Perrault 2007](#)). Both the homozygous and heterozygous genotypes result in a similar clinical presentation. The *CEP290* p.Cys998X

mutation appears to be hypomorphic in nature, with wild-type transcripts present in peripheral tissues, explaining the non-syndromic nature of the *CEP290* p.Cys998X mutation ([Parfitt 2016](#)).

